- Carolina Data Warehouse for Health (CDW-H) (for UNC and its affiliates only)
- Carolinas Collaborative Data Request and Review Committee (DRRC)
- Paper medical records

If you access the records of fewer than 50 patients under a full or limited waiver of HIPAA, submit a copy of your IRB approval letter and a completed [Research Disclosure Form](#) to Health Information Management (HIM). Do not submit this information to the IRB. For additional information about this process, you should contact HIM directly at : [contact] or [contact] or [contact].

- Data already collected from another research study

Were the investigators for the current application involved in the original collection?	--
---	----
- Patient specimens (tissues, blood, serum, surgical discards, etc.)

Has the clinical purpose for which they were collected been met before removal of any excess?	--
---	----
- Data already collected for administrative purposes
- Student records (You will need to satisfy FERPA requirements: see SOP 2301, section 1.1 for guidance)
- UNC Dental Records
- Data coming directly from a [health plan, health care clearinghouse, or health care provider?](#)
- Publicly available data
- Other
- None of the above

For EACH data source checked above, provide a description of the data, proposed use, how data were collected (including consent procedures), and where data currently reside.

--

IRB Number: 17-2655 Initial Principal Investigator: [name]

C.1.2. Describe your plans for obtaining permission from the custodians of the data, records or specimens (e.g., pathology dept, tissue bank, original researcher):

No Answer Provided

C.1.3. Do the custodians of the data, records or specimens require a data use agreement?

No

C.2. Coding and Data Use Agreements

C.2.1. When you receive these data, records or human biological specimens will they be coded? Coded means identifying information that would enable the research team to readily ascertain the individual's identity has been replaced with a number, letter, symbol, or combination thereof (i.e., a code). If you will not be using existing materials, check "No."

No

Answer the questions below to identify the mechanism which precludes your access to the codes and include a copy of any agreements or documents that explain these protections:

Data use agreement with custodian of data (agreement prohibiting the release of the key to decipher the code to the applicant under any circumstances)?	--
Note: For Data Use Agreements, Non-Clinical Agreements, or Clinical Agreement Amendments, please submit the New OIC RRF and draft materials via email to [contact]	--
Data are publicly available?	--
Honest broker (centralized custodian who controls data and will not release codes or IDs)?	--
Other	--

Part D. The Consent Process

D.1. Obtaining informed consent from subjects

The standard consent process is for all subjects to sign a document containing all the elements of informed consent, as specified in the federal regulations. Some or all of the elements of consent, including signatures, may be altered or waived under certain circumstances. If you will be requesting a waiver answer "not applicable" for any of the following questions that will not pertain to this study. You will be asked to provide relevant information in the section below on waivers.

D.1.1. Will children under the age of majority in their locale (18 years in NC) be enrolled?

(Note: Any minor subject who attains the age of majority during the course of the research study must provide consent as an adult, unless consent has been waived, which is requested in section D.3.1.)

No

D.1.2. Will adult subjects be enrolled in your study?

Yes

Explain the process for obtaining consent from the subject.

Phase 1: Prior to completion of the electronic eligibility survey, potential participants will read a description of the information that will be gathered in the surveys and the purpose of that information. Potential participants will then be asked to provide consent for this element (screening for eligibility) of the study. If consent is not provided, they will be thanked for their time and interest and told that they are not eligible for the remaining parts of the investigation. Phase 2: Once deemed eligible, potential participants will be contacted to schedule the testing session. Upon reporting to the Sports Medicine Research Center and prior to data collection, all subjects will be required to read and sign the approved informed consent form. Individuals will be asked if they have any questions pertaining to the study procedures prior to signing the consent form and initiating data collection.

D.1.3. Will decisionally-impaired subjects be enrolled in your study? (includes unconscious patients, some psychiatric disorders, others who lack the capacity to give consent)

No

D.1.4. Are you planning to obtain consent from any Non-English speaking subjects?

No

D.1.5. Describe who (by role) will be obtaining consent or parental permission.

Consent will be obtained only by those personnel listed on the protocol.

D.1.6. Discuss the potential for influencing the subject's decision to participate. Describe steps that will be taken to minimize undue influence during the consent process. These might include a waiting period between the initial consent discussion and obtaining consent, or obtaining consent by someone other than a person with perceived authority (e.g., professor, employer, treating physician).

As the PI teaches courses in which potential subjects may be currently enrolled or enrolled in the future, these individuals will be informed that their participation or the lack thereof will not influence their grade in a given course or their academic standing.

IRB Number: 17-2655 Initial Principal Investigator: [name]

The following language will also be placed on the informed consent and discussed during recruitment.

What if you are a UNC student?

You may choose not to be in the study or to stop being in the study before it is over at any time. This will not affect your class standing or grades at UNC-Chapel Hill. You will not be offered or receive any special consideration if you take part in this research.

What if you are a UNC employee?

Taking part in this research is not a part of your University duties, and refusing will not affect your job. You will not be offered or receive any special job-related consideration if you take part in this research.

D.1.7. Has the sponsor of this study provided a model consent form?

No

D.2. Waiver of written documentation of informed consent

The default is for subjects to sign a written document that contains all the elements of informed consent. Under limited circumstances, the requirement for a signed consent form may be waived by the IRB. For example, this might occur for phone or internet surveys, when a signed consent form is either impractical or unnecessary, or in circumstances where a signed consent form creates a risk for the subject.

D.2.1. Are you requesting a waiver of any aspect of written (signed) documentation?

Yes

Choose which of the following consent approaches apply and attach the relevant document: *

Full consent form minus the signature lines

You will be provided with a system built consent form when you reach the Consent Form section. This can be edited to remove the signature lines.

Information or fact sheet (streamlined unsigned consent form)

Online consent form with electronic agreement

Consent statement incorporated into a survey itself

Verbal consent obtained in person or via the phone

Short form (for subjects with limited ability to read full consent form)

Choose which one of the following justifies the waiver of written documentation: *

The only record linking the subject and the research would be the consent document and the principal risk would be potential harm resulting from a breach of confidentiality (e.g., study topic is sensitive so that public knowledge of participation could be damaging). Participants should be asked whether they want documentation linking them with the research and the participants' wishes will govern whether they sign the form. Note: This justification cannot be used in FDA-regulated research.

The research presents no more than minimal risk of harm to subjects and involves no procedures for which written consent is normally required outside of the research context. (e.g., many phone or mail surveys, "man in the street" interviews, etc.).

Explain

The study is broken into two phases. The first is an online survey to determine eligibility. Participants are informed of what will be collected in the survey and that they do not have to complete the survey (elements of consent are present) but participants cannot give a written consent. Therefore, we are requesting a partial waiver for pre-screening of potential participants. The text that includes some elements of consent can be found in the eligibility packet submitted with this application.

If your request for a waiver of written documentation applies to some but not all of your subject groups and/or consent forms, please describe and justify

No Answer Provided

D.3. Full or partial waiver of consent

The default is for subjects to give informed consent. A waiver might be requested for research involving only existing data or human biological specimens. More rarely, it might be requested when the research design requires withholding some study details at the outset (e.g., behavioral research involving deception). In limited circumstances, parental permission may be waived. This section should also be completed for a waiver of HIPAA authorization if research involves Protected Health Information (PHI) subject to HIPAA regulation, such as patient records.

D.3.1. Are you requesting any of the following:

a waiver of informed consent in its entirety

a waiver or alteration of some of the elements of informed consent

a waiver of HIPAA authorization (If you are accessing patient records for this research, you must also request a waiver of HIPAA authorization)

IRB Number: 17-2655 Initial Principal Investigator: [name]

D.3.2. If your request for a waiver applies to some but not all of your subject groups and/or consent forms, please describe and justify
 No Answer Provided

D.3.3. Does this request for waiver support a study design that involves deception or withholding of information?
 No

Consent Forms

This submission requires the following consent forms

Template Type

Adult Consent Form

Text for Online Consent Form

I am not using this template because: Waiver of written consent requested in application (Section D.2.)

This submission includes the following consent forms

File Name

Adult_Consent_Form-1_BIO of MT_R1.docx

Document Type

Adult Consent Form

[view consent forms](#)

Attachments

This submission requires the following attachments

Document Type

Grant Application

Electronic Questionnaire Survey

Script for Class Recruitment

Flyer for Recruitment

Email or Listserv Recruitment

This submission includes the following attachments

File Name

COMBINED GRANT_NO CITATION FIELDS.docx

Class Recruitment_Bio of MT.docx

Email Recruitment_Bio of MT.docx

Flyer_Bio of MT.docx

Eligibility Packets_Bio of MT.docx

RE R21AT009704-01 clarification letter.txt

Document Type

Grant Application

Script for Class Recruitment

Email or Listserv Recruitment

Flyer for Recruitment

Electronic Questionnaire Survey

Email Correspondence (convert to PDF or TXT)

[view attachments](#)

Addenda

 Data Security Requirements

[view addenda](#)

IRB Number: 17-2655

Initial

Principal Investigator: [name]

If Principal Investigator of this study is a Student or Trainee Investigator, the Faculty Advisor certifies the following:

I accept ultimate responsibility for ensuring that this study complies with all the obligations listed above for the PI.

By certifying below, the Principal Investigator affirms the following:

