Participants will be randomized to one of the three groups (Massage, Joint Mobilizations, or Control) in a 1:1:1 ratio using sealed envelopes generated by the biostatistician. More specifically, we will be using a block randomization technique at each institution so that preliminary data analysis, data monitoring, and safety evaluations will be based on similar, if not identical, numbers in each group. Each block of envelopes will be made and sealed before study enrollment begins and randomization will occur after the baseline evaluation (see section 9.b of Appendix 1). The biostatistician will generate the master randomization list and distribute the envelopes. Each participant will select a sealed envelope containing their group assignment. This assignment will be noted by the research team and recorded.

SECTION I: Blinding / Unblinding

SECTION I: Blinding / Unblinding

SECTION I: Blinding / Unblinding

As per section 11 of Appendix 1 blinding will be used in the current investigation. Due to the nature of the intervention, participants will not be blinded but the assessors of the outcome measures will be blinded to group assignment.

SECTION J: Study Intervention

SECTION J: Study Intervention

The treatments as outlined in section 9.c of Appendix 1 will include:

Sensory-Targeted Rehabilitation Strategies. This intervention will consist of 6, 5-minute treatments the following over a 2-week period:

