Neuromuscular mechanisms will be quantified before and immediately after a 2-week intervention. Mechanisms will include a comprehensive group of peripheral (ankle joint position sense, plantar light-touch discrimination thresholds), spinal (H-reflex of the soleus and fibularis longus), and supraspinal measures (cortical activity during stance using electroencephalography [EEG], corticomotor excitability and mapping of the soleus and fibularis longus via transcranial magnetic stimulation [TMS], and sensory organization strategies during stance). Our primary mechanism of interest is sensory organization strategies. Sixty CAI patients will be randomized into three equal groups (ankle joint mobilization, plantar massage, control) to complete 6 treatment sessions over 2-weeks.

Hypothesis 1. Both interventions, relative to the control group, will result in significant sensory organization strategy changes, representing a reduction in the CAI patient's reliance on visual information during stance.

Hypothesis 2. Each intervention will result in unique combinations of peripheral, spinal, and supraspinal mechanistic pathways relative to the control group.

Aim 2: Determine the associations among peripheral, spinal, and supraspinal neuromuscular mechanisms, secondary biomechanical measures, and sensory organization strategies in CAI patients. These associations will be quantified to elucidate the unique combination of peripheral, spinal, and supraspinal mechanistic pathways thought to contribute to a reducing in the reliance of visual information during stance. Secondary measures which will include jump landing and gait biomechanics will be assessed before and immediately after the 2-week interventions. We will use an analytical approach (see statistical analysis) to determine simple associations at baseline, post-test, and among change scores in neuromuscular mechanisms and secondary measures.

Hypothesis 1. Each intervention will result in unique combinations of changes in peripheral, spinal, and supraspinal mechanistic pathways will be strongly associated with changes sensory organization strategies.

Hypothesis 2. Each intervention will result in secondary measure changes associating with changes in sensory organization strategies as well as peripheral, spinal, and supraspinal mechanistic pathways.

3 Study Design

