We plan to use a single-blind randomized study design to quantify changes in the hypothesized neuromuscular mechanisms following ankle joint mobilization and plantar massage. Assessors will be blinded to group assignment.

4 Primary & Secondary Endpoints

This study will have 1 primary endpoint at the conclusion of the 2-week intervention. This study will have 1 secondary endpoint 1-month after the conclusion of the 2-week intervention. All outcomes will be assessed at both endpoints.

5 Type & Number of Sites

A total of 1 site will be used during this study: the University of North Carolina at Chapel Hill.

6 Patient Population & Numbers

Only those with CAI, as defined by the International Ankle Consortium (IAC) will be enrolled. Specific inclusion criteria will be identical to our previous work and consist of a history of at least two episodes of “giving way” within the past 6 months; scoring ≥ 5 on the Ankle Instability Instrument (AII), scoring $\leq 90\%$ on the Foot and Ankle Ability Measure (FAAM), and scoring $\leq 80\%$ on the FAAM Sport (FAAM-S). Exclusion criteria

will consist of acute ankle sprains <6 weeks, previous ankle surgeries, lower extremity surgeries associated with internal derangements, and conditions affecting neuromuscular control.

Changes in sensory organization strategies has been chosen as the primary mechanism of interest and will be assessed by calculating the % Modulation of the resultant center of pressure velocity between eyes open and eyes closed stance.³³

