To achieve Aim 1, 18 participants per group are needed to ensure significant changes in the primary mechanism of interest following both interventions relative to the control group. Between group (i.e. massage vs. control [$d=0.53$] & mobilization vs. control [$d=0.69$]) pre to post effect sizes from our preliminary data (See Preliminary Studies) were used to calculate the needed sample size. Using GPower (3.1), a repeated measures, between factors ANOVA model for three groups and two time points was used. Parameters included a purposefully conservative intra-measure correlation= 0.90 , $\alpha=0.05$, and $1-\beta=0.90$. To achieve Aim 2, 16 participants per group are needed to identify significant correlations. This value was calculated based on previously established correlations between neuromuscular mechanisms and biomechanical measures of postural control.^{16, 95} Parameters for this analysis included a correlation of $r=0.5$ (range from literature: 0.50 to 0.58), an $\alpha=0.05$, and $1-\beta=0.90$. Thus, we will recruit 20 participants per group and plan for a 10% dropout rate, which would leave 18 subjects per group. Our previous work⁴² had a 98.75% (79/80) retention rate using the same intervention protocol and all participants completed 100% of the treatment sessions.

7 Inclusion & Exclusion Criteria

Inclusion criteria will consist of the following:

- Male or female 18-45 years of age
- History of ankle sprain with at least two episodes of “giving way” within the past six months
- Score of ≥ 5 on the Ankle Instability Instrument (All)
- Score of $\leq 90\%$ on the FAAM-ADL
- Score of $\leq 80\%$ on the FAAM-S.

Exclusion criteria will consist of the following:

- Younger than 18 or older than 45 years
- No history of ankle sprain or episodes of “giving way” in the past six months
- Score of ≤ 5 on the Ankle Instability Instrument (All)

- Score of $\geq 90\%$ on the FAAM-ADL
- Score of $\geq 80\%$ on the FAAM-S.
- An acute ankle sprain within the past 6 weeks.
- Previous history of lower extremity surgery with internal derangements, reconstructions, or repair
- Lower extremity injury within the past 6 months (other than ankle sprains)
- Presence of balance deficits or conditions known to affect balance as noted on the Balance Questionnaire including diabetes and/or vertigo.

8 Randomization Plan

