Participants will be randomized to one of groups in a 1:1:1 ratio after stratification based on treatment expectation responses. This process will happen using sealed envelopes prepared by the study biostatistician. More specifically, we will be using a block randomization technique at each institution so that preliminary data analysis, data monitoring, and safety evaluations will be based on similar, if not identical, numbers in each group. Each block of envelopes will be made and sealed before study enrollment begins and randomization will occur after the baseline evaluation (see section 9.b below). The biostatistician will be responsible for generating the master randomization list and each participant will select a sealed envelope containing their group assignment. This assignment will be noted by the PI and recorded. Assessors will be blinded to group assignment.

9 Screening Process, Baseline Evaluation, Study Treatment, & Final Evaluation

9.a Screening Process

The screening process will be performed at a specific eligibility screening session. At this session, potential participants will complete the Balance Questionnaire (Appendix 2), All (Appendix 3), FAAM (Appendix 4), FAAM-Sport (Appendix 4), and Treatment Expectation (Appendix 5) questionnaires. If eligible, participants will be scheduled for baseline testing which will be the first of 3 testing sessions. The first will take place on the day of baseline evaluation. The second will take place at the end of the 2-week intervention. The third will take place 1-month after the final treatment session.

9.b Baseline & Post-Test Evaluations

The baseline evaluation will include gathering general information regarding age, height, leg length, foot measurements, weight. Participants will then receive instruction on the testing procedures and will perform several warm-up trials on all assessments to become familiarized with the testing procedures. Next, participants will have their ankle range of motion, postural control, and lower extremity biomechanics tested. Finally, participants will complete the possible neuromuscular mechanism measures. All outcomes will be performed at all test sessions. More detailed descriptions are provided below:

[figure not shown]
Peripheral Neuromuscular Mechanisms:

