Intervention Delivery: After completion of baseline testing, participants will be randomized into 3 groups to receive interventions identical to our previous work.^{42, 71} All interventions are to a single limb and require 6, 5-minute treatment sessions over 2-weeks. The first group (n=20) will receive 2, 2-minute bouts of Grade III anterior-to-posterior talocrural joint mobilization with 1-minute between sets during each session. Mobilizations will be large-amplitude, 1-5 rhythmic oscillations from the mid- to end range of arthrokinematic motion. The second group (n=20) will receive 2, 2-minute plantar massage bouts with 1-minute between sets during each session. The massage will be a combination of petrissage and effleurage to the entire plantar surface. The third group (n=20), a control condition, will receive no treatment during the entire 2-week intervention period. All groups will be instructed to continue regular physical activity habits and daily routines over the course of 2-week intervention.

A.4.3. If subjects are assigned or randomized to study "arms" or groups, describe how they are assigned.

- Describe the methods of computing the randomization schedule (if any) and maintaining blinding (if any).
- Who will perform these computations?
- How will you verify each subject's eligibility prior to randomization?

Participants will be randomized and allocated in a 1:1:1 ratio within blocks (n=6) using sealed envelopes generated by the study biostatistician.

IRB Number: 17-2655	Initial	Principal Investigator: [name]
---------------------	---------	---------------------------------------

Eligibility will be determined by questionnaire, consistent with best practices research within the field of chronic ankle instability.

A.4.4. Describe any follow up procedures.

A 4-week follow up after the intervention will be conducted. This assessment is identical to those conducted immediately before and after the intervention and is described above in A.4.2.

A.4.5. Once this study has been approved by the IRB, for how many months or years will this study be active (you are collecting data or have access to identifiers)?

36-months.

A.4.6. Will this study use any of the following methods?

 Audio Recording
 Video Recording

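### A stated fixed block of 6, with participant-selected envelopes and no stated numbering or opening log, could let staff know up to about one in five assignments in advance

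*Combined protocol and SAP*

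**What the plan says.** - **Block size.** Appendix 18, A.4.3 is the only place that gives one: "Participants will be randomized and allocated in a 1:1:1 ratio within blocks (n=6) using sealed envelopes generated by the study biostatistician". Section H, K.2.b and Appendix 1 Section 8 describe blocking without a size.
- **Size and sites.** "Sixty CAI patients will be randomized into three equal groups" (Appendix 1, Section 2). "A total of 1 site will be used during this study" (Appendix 1, Section 5), although Section H and Section 8 still speak of blocking by institution.
- **Envelopes.** Section 8: "each participant will select a sealed envelope containing their group assignment". Section H and K.2.b say the same. Nothing says that envelopes are opaque, numbered, opened in sequence or logged on opening. The biostatistician does generate a master list.
- **Who learns the assignment.** Section H: "This assignment will be noted by the research team and recorded". In Section 8 and K.2.b it is the PI who notes it.
- **Block ends.** Appendix 18, A.7.1 has the PI complete a progress report for each finished block.
- **Strata.** Section 8 and K.2.b stratify on treatment-expectation answers but define no strata. Section H and A.4.3 do not mention stratification.
- **Blinding and timing.** "Assessors will be blinded to group assignment" (Appendix 1, Section 3); participants are not blinded (Section I). Randomisation follows baseline testing.

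**The concern.** With a constant, known block size and visible block ends, anyone who has seen the earlier assignments in a block knows the last one, and sometimes the last two. Here the people who record assignments also schedule participants, and Section D.1 trains all staff both in data collection and in the randomisation process.

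Foreknowledge could influence which eligible person is booked next. Because the envelope is opened after baseline, it could also affect how baseline is tested. Aim 1 compares change from baseline, so a shaded baseline feeds directly into the result.

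Participant selection is a second weakness. If the participant chooses freely among envelopes, the order of the master list is not followed, and no stated record would show which list position each person received.

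**Working it through.** **Inputs.** Block of 6 at 1:1:1, so 2 per arm (A.4.3). Recruitment: "we will recruit 20 participants per group and plan for a 10% dropout rate, which would leave 18 subjects per group" (Appendix 1, Section 6).

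**Plan's own figure.** 18 / (1 − 0.10) = 20 per arm; 3 × 20 = 60; 60 / 6 = 10 blocks. This reproduces. The plan gives no figure for predictability.

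**1. One unstratified stream, issued block by block.** An assignment is certain when all remaining places in the block belong to one arm. With m places per arm and three arms, the expected number certain is 3m / (2m + 1).
- m = 2: 6/5 = 1.2 of 6 = 20%, or 12 of 60.
- By position: the sixth is always certain. The fifth is certain when the last two places share an arm: 3 / C(6,2) = 3/15 = 1/5.
- At least one arm is excluded with probability 1/5 at position 3, 1 − 8/20 = 3/5 at position 4, and 1 at positions 5 and 6: 0.2 + 0.6 + 1 + 1 = 2.8 of 6.
- Best guess by position: 1/3, 2/5, 1/2, 8/15, 3/5, 1. The mean is 56.1%, against 33.3% by chance.

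Enumerating all 90 orderings of a block gives the same values. Choosing freely *within the current block* changes nothing.

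**2. Choice from the whole pool of 60.** m = 20: 60/41 = 1.46 of 60 = 2.4% certain. The blocks then no longer control balance during recruitment.

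**3. Stratified blocks of 6.** Number of strata assumed, strata equally likely and known to staff; simulation:

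| Strata | Certain |
|---|---|
| 1 | 20.0% |
| 2 | 18.5% |
| 3 | 17.7% |
| 5 | 16.1% |
| 8 | 13.9% |
| 15 | 7.2% |
| 27 | 1.7% |

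**4. Randomly varying sizes.** Staff know the set of sizes but not the draw. Certain assignments, one stream: 8.6% for sizes 3 and 6; 5.0% for 6 and 9; 3.7% for 3, 6 and 9. A fixed block of 9 would still give 9/7 of 9 = 14.3%. With 2 to 5 strata, sizes 3 and 6 give about 7–8%.

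**5. Balance at 60.** Share of simulated trials in which two arms differ by more than two:

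| Blocks | 1 stratum | 2 | 3 | 5 |
|---|---|---|---|---|
| Fixed 6 | 0% | 7% | 16% | 37% |
| 3 and 6 | 0% | 4% | 12% | 30% |
| 6 and 9 | 1% | 12% | 24% | 43% |

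**6. A limit of the remedy.** I also simulated a guesser who weights each block size by its probability given the assignments seen so far (one stream). The best guess is right about 58% of the time with sizes 3 and 6, and 54% with 6 and 9, against 56% for fixed 6. Varying sizes removes certainty; it does not make guessing much harder.

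**The case against.** **One in five is a ceiling, not an estimate.** This stands. The current protocol text stratifies, and it does not say how envelopes are laid out. The 20% needs a single stream issued by block.

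**The block size may be out of date.** It appears only in the IRB application received in October 2017, which differs from the manual elsewhere: REDCap rather than Sharepoint, and no monitoring committee. This also stands in part. Still, no other size is given and the application is part of the current document, so it is the stated method.

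**A reader might infer that assessors can work out the arm.** The documents do not support that. Assessors are stated to be blinded, and deduction requires the earlier assignments in the block. The treatment-group field on the data collection sheet (Appendix 17) is a separate threat to blinding, which varying the blocks would not cure.

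**A reader might infer that there is no audit trail.** That is too strong. A master list exists and each assignment is recorded. What is not stated is a number, order or log linking the two.

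**There is little room for selection.** Eligibility rests on questionnaire cut-offs, and consent and baseline testing come before randomisation. This narrows the risk but leaves scheduling and the conduct of baseline testing open.

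**Varying blocks costs balance.** True of 6 and 9 when stratified. It is not true of 3 and 6, which balance no worse than fixed 6 in the simulation.

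**Conclusion.** The point holds as a minor design weakness. Up to about 20% of assignments (12 of 60) could be known in advance to the PI, treating staff or whoever records them. This assumes that the block of 6 applies, that envelopes are issued block by block in one unstratified stream, and that block ends are known. With 2 to 5 equal strata it is about 16–19%, and less with more. With choice from the whole pool it is 2.4%, at the price of the balance that blocking was meant to give. Neither arrangement of participant selection is satisfactory, and the text does not say which is meant. Nothing here shows that bias would occur, and the sample size and analysis are unaffected.

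**What to change.** - **Appendix 18, A.4.3:** replace the fixed block of 6 with randomly varying block sizes known only to the biostatistician, applied within each expectation stratum used in Section 8 and K.2.b. Sizes 3 and 6 cut certain assignments to about 9% or less without worsening arm balance. Sizes 6 and 9 give about 5%, with somewhat more imbalance when stratified. Keep the actual sizes out of documents the study team holds.
- **Appendix 18, A.7.1:** tie progress reports to the calendar (a six-month minimum is already there) rather than to completed blocks, which would disclose the block ends.
- **Section H, Appendix 1 Section 8 and K.2.b:** replace participant selection with opening the next sequentially numbered opaque envelope, and log its number and date against the master list.

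Cost: a new list and envelope set before enrolment, and arm sizes that may differ slightly at the end. In-order opening and the log bring benefit whichever block sizes are chosen.
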